13.9 Early withdrawal

If a patient is withdrawn from the study early they will continue with their standard care at the unit.

It will be documented in the CRF and medical notes if the patient is happy to continue on with study visits (without the study medication), or continue to have their clinical data collected, or no further data collected.

13.10 End of trial (EOT)

It is the CI's responsibility to submit the EOT notification to REC and MHRA once obtaining sponsor approval. The EOT notification must be received by REC and MHRA within 90 days of the end of the trial.

If the study is ended prematurely, the Chief Investigator will notify the Sponsor, REC & MHRA including the reasons for the premature termination (within 15 days).

End of Trial definition: is after the last patient has completed their last follow up point at 1 year post-transplant (data review visit).

14.0 Laboratories and samples

14.1 Local Laboratories

Standard biochemistry samples will be sent to the Royal London Hospital Laboratory. All the tests that will be performed are part of the standard diagnostic set of tests commonly used to test for diabetes.

Research blood samples will be taken at the same time, labelled with the patient's study number and date of sampling. They will be taken to the Immunology laboratories at the Royal London Hospital in order to isolate and store the patient's peripheral blood cells. Flow cytometry analysis of peripheral T cell populations will take place in the Immunology laboratories. Stored peripheral blood cells may also be taken to the William Harvey Research Institute by members of the study team, for functional analysis of peripheral Treg populations and analysis of inflammatory signalling markers. The serum save will be taken and processed in keeping with normal protocols in the Royal London Hospital Laboratory but will be taken to either the Royal London Immunology laboratories or the William Harvey Research Institute to be used in functional assays to measure the activity of the Tregs at different time points.

In addition, renal biopsy tissue collected as part of standard of care at the time of transplant and at month 3 will be examined for Treg cell infiltration. If any renal biopsies are carried out for a clinical indication in the interim period, then these will also be examined for Treg cell infiltration.

14.2 Sample Collection/Labelling/Logging

Samples will be collected by the research nurse or trained phlebotomist as per standard of care.

Samples will be labelled with patient identification and sent to the local labs as per routine care and the results logged on the pathology system and transcribed to the CRF.

The only samples that will be sent to the local lab, which are not part of routine care, are for serum C-peptide.

Volume of samples to be collected:

The total volume of blood which will be taken on top of routine care is:

1 table-spoon (approximately 20ml) of blood per clinic visit (4x 6ml samples of blood) in lithium heparin tubes provided locally.

In addition, 20ml of blood will be taken at visit 1, 2, 6 and 7 for Treg quantification via FACS. This sample will be taken to the Royal London Immunology laboratories by members of the study team for processing.

Any biopsy material will be processed and stored as part of routine clinical care.

14.3 Sample Receipt/Chain of Custody/Accountability

Samples will be sent to the lab by the research nurse, where they will be processed as per the lab's standard SOPs under their UKAS accreditation. The research team will have responsibility for the custody of the samples until they are handed over the lab technicians at the sample collection point. Research blood samples will remain within the custody of the research team.

14.4 Sample Analysis Procedures

All standard (biochemistry, haematology) samples will be taken to the local lab by the research nurse/team after being taken. All samples will be processed in accordance with local procedures.

In addition, research blood samples will be taken at the same time, labelled with the patient's study number. The isolation and FACS analysis of peripheral blood cells will be performed by members of the study team as per the Immunology lab's standard SOPs.

Peripheral blood cell samples and stored serum may also be taken to the William Harvey Research Institute by members of the study team, for functional analysis of peripheral T cell populations and analysis of inflammatory signalling markers. After sample processing is completed the samples will be destroyed and not stored further.

14.5 Sample and Data Recording/Reporting

Data will be recorded on the CRF/eCRF.

The CRF will be completed by the CI, SUB-I or research nurse. The CI will countersign completed CRFs and these will be stored securely in the study file in the research office.

14.6 End of study

No biological material will be kept in the department. All biological samples will have been sent to the lab and disposed of as per their routine SOP. No biological samples

will be retained at William Harvey Research Institute: they will be destroyed after sample processing.

15.0 Trial Medication

15.1 Name and description of investigational medicinal product(s)

AZD1656 is a potent and selective glucokinase activator that is administered orally as a tablet formulation. The matching placebo tablets have the same appearance as the tablets containing AZD1656.

15.2 Legal status of the drug

Not licenced

15.3 Summary of Product Characteristics (SmPC) or IB

See IB Edition 9, Sept 15th 2020

15.4 Drug storage and supply

The IMP/placebo will be shipped securely to the clinical trials pharmacy unit from the pharmacy manufacturing unit, where it will be stored until needed. The research nurse will collect the IMP/placebo from the clinical trials pharmacy and give this to the study patients. All medicinal products left over after study completion will be destroyed.

15.5 Supplier

The IMP and placebo will be packed and labelled by Fisher Clinical Services and sent to the clinical trials pharmacy at the Royal London Hospital.

Fisher Clinical Services U.K. Limited [name] United Kingdom

The supply is being made specifically for use in the trial, and will not be used for any other purpose then as stated in the trial.

15.6 Manufacturer

The tablets were manufactured by Patheon.

Patheon UK Limited

[name] United Kingdom

15.7 IMP Storage

The drug should not be stored above 25°C or stored anywhere other than in the original package. The containers should be kept tightly closed.

The shelf life of the drug will be updated based on read-outs from an on ongoing stability study. The initial shelf life will be at least 12 months.

There are no special arrangements needed for the storage of the medication (it can be stored at room temperature).

15.8 Details of accountability

The study medication will be dispensed from pharmacy and given to the patient by a member of the research team on the delegation log. An accountability log will be used to record the details of each batch of study medication dispensed to a patient, including subject identification code, drug batch number, date of dispensing and quantity dispenses, date returned and quantity returned, and date destroyed. Accountability logs will be maintained by the clinical trial pharmacist.

15.9 Medication destruction/return and recall

At month 3 any unused study medication will be returned, counted and then destroyed as per local policy.

15.10 Prescription of IMP / Placebo/ NIMP

The ADOPTION prescription form will be used to prescribe IMP or placebo.

15.11 Preparation and labelling of IMP and Placebo

The active treatment is AZD1656 50mg tablets. The placebo tablet contains no active ingredient and is a visual match to the active.

The IMP and placebo will be packed and labelled by Fisher Clinical Services and sent to the clinical trials pharmacy at the Royal London Hospital.

Fisher Clinical Services U.K. Limited [name] United Kingdom

15.12 Preparation and Administration of IMP

The IMP will be dispensed as 50mg tablets with two to be taken twice a day. Patients will be counselled on their dose during visit 1.

15.13 Dosage schedules

The patient will be dispensed either placebo or AZD1656 tablets for a 3 month supply.

These are two 50mg oral tablets to be taken twice a day with or after meals.

Missed doses will be permitted: if a patient misses a dose they should take their next dose at the usual time. Drug adherence will be encouraged at each visit. Drug accountability will be assessed at each study visit where patients will bring back their unused supply with non-adherence defined as less than 80% or more than 120% of medications taken.

15.14 Dispensing of IMP

There will be a dispensing guideline in place within pharmacy. Each member of staff who dispenses the IMP will sign the local/pharmacy dispensing log to document appropriate IMP tracking. All members of the trial team should ensure that they have had study specific training and their involvement should be demonstrated by the study specific trial delegation log.

15.15 Dosage modifications

No dosage modifications will be allowed.

However the study medication may be stopped if the investigator feels it is not safe for the patient to continue treatment with the study medication. At this point the patient will be withdrawn from the treatment with study medication for the rest of the trial but will continue in all other study related activities.

15.16 Known drug reactions and interaction with other therapies

Gemfibrozil is a potent inhibitor of the isoenzyme CYP2C8. When AZD1656 was administered as a single dose together with gemfibrozil, a 2.7-fold increase in AUC of AZD1656 was observed compared to single dose administration of AZD1656 alone. The $t_{1/2}$ of AZD1656 increased, suggesting that AZD1656 will accumulate by approximately 50% following repeated twice daily dosing of AZD1656 to steady state during concomitant gemfibrozil administration. However, the levels of the active metabolite, AZD5658, were reduced during co-administration with gemfibrozil. No statistically significant increase was observed for C_{max} when dosed together with gemfibrozil (D1020C00030).

15.17 Prior and Concomitant medication

Given the theoretical increase in AUC (but not C_{max}) with gemfibrozil. Any patient who is currently taking this agent will be excluded from the study.

Prior and Concomitant medication lists will be recorded in the case record forms

15.18 Assessment of compliance

Compliance will be assessed at study visits, when the research team will count the number of tablets returned and consider less than 80% or more than 120% adherence to be non-compliant.

15.19 Arrangements for post-trial access to IMP and care

This agent will not be available for long-term use as published studies have shown that its biological effect wears off after 3-4 months.

16 Equipment and Devices

No equipment or devices will be used outside of standard care.

17 Pharmacovigilance

17.1 General Definitions

Term	Definition
Adverse Event (AE)	Any untoward medical occurrence in a participant to whom a medicinal product has been administered, including occurrences which are not necessarily caused by, or related to, that product.
Adverse Reaction (AR)	An untoward and unintended response in a participant to an investigational medicinal product which is related to any dose administered to that participant.
	The phrase "response to an investigational medicinal product" means that a causal relationship between a trial medication and an AE is at least a reasonable possibility: i.e. the relationship cannot be ruled out.
	All cases judged by either the reporting medically qualified professional or the Sponsor as having a reasonable suspected causal relationship to the trial medication qualify as adverse reactions.
Serious Adverse Event (SAE)	 A serious adverse event is any untoward medical occurrence that: Results in death. Is life-threatening. Requires inpatient hospitalisation or prolongation of existing hospitalisation. Results in persistent or significant disability/incapacity. Consists of a congenital anomaly or birth defect.
	Other 'important medical events' may also be considered serious if they jeopardise the participant or require an intervention to prevent one of the above consequences.
	NOTE: The term "life-threatening" in the definition of "serious" refers to an event in which the participant was at risk of death at the time of the event; it does not refer to an event which hypothetically might have caused death if it were more severe.
Serious Adverse Reaction (SAR)	An adverse event that is both serious and, in the opinion of the reporting Investigator, believed with reasonable probability to be due to one of the trial treatments, based on the information provided.
Suspected Unexpected Serious Adverse Reaction (SUSAR)	 A serious adverse reaction, the nature and severity of which is not consistent with the information about the medicinal product in question set out in the Reference Safety Information (RSI): In the case of a product with a marketing authorisation, in the summary of product characteristics (SmPC) for that product. In the case of any other investigational medicinal product, in the investigator's brochure (IB) relating to the trial in question.

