17.2 Site Investigators' Assessment

The Chief Investigator is responsible for the care of the participant, or in his/her absence a delegated medical practitioner and is responsible for assessment of any event for:

• Seriousness

Assessing whether the event is serious according to the definitions given in section 17.1.

Causality

Assessing the causality of all serious adverse events/reactions in relation to the trial treatment according to the definition given. If the SAE is assessed as having a reasonable causal relationship, then it is defined as a SAR.

• Expectedness

Assessing the expectedness of all SAEs according to the definition given. If the SAE is unexpected, then it is a SUSAR.

• Severity

Assessing the severity of the event according to the following terms and assessments. The intensity of an event should not be confused with the term "serious" which is a regulatory definition based on patient/event outcome criteria.

- o Mild: Some discomfort noted but without disruption of daily life
- o Moderate: Discomfort enough to affect/reduce normal activity
- Severe: Complete inability to perform daily activities and lead a normal life

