17.7 Notification and Reporting of Serious Adverse Events & SUSARs

All Serious Adverse Events (SAEs) will be recorded in the participants' notes, the CRF, the sponsor SAE form, and reported to the sponsor (Joint Research Management Office) within 24 hours of the CI or co-investigators becoming aware of the event. Nominated co-investigators (as listed in the delegation log) will sign the SAE forms in the absence of the CI.

Reporting of SUSARs

Suspected Unexpected Serious Adverse Reactions (SUSARs) that occur during the trial will be reported to the sponsor (joint management research office) within 24 hours of the CI or co-investigator becoming aware of the event. The sponsor will then report this to the MHRA.

Reporting of SAE/SUSAR to Astra Zeneca (see appendix 1: Safety Reporting Responsibilities)

Report unblinded Suspected Unexpected Serious Adverse Reactions (SUSARs) to AstraZeneca (via Kinapse) as individual case reports as they occur.

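### Sections 17.1 and 17.2 give different answers on whether a serious, unexpected event that is possibly but not probably related to treatment is a SUSAR

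*Combined protocol and SAP*

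**What the plan says.** The table in section 17.1 defines three nested terms.

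- **Adverse reaction.** A causal link to the trial medication "is at least a reasonable possibility: i.e. the relationship cannot be ruled out". On who decides, the row adds that "All cases judged by either the reporting medically qualified professional or the Sponsor as having a reasonable suspected causal relationship" to the medication count as adverse reactions.
- **Serious adverse reaction.** An event that is serious and, in the reporting investigator's opinion, "believed with reasonable probability to be due to one of the trial treatments". The sponsor is not mentioned.
- **SUSAR.** "A serious adverse reaction, the nature and severity of which is not consistent with the information about the medicinal product in question", as set out in the reference safety information.

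Section 17.2 then tells the assessor how to classify an event. For causality: "If the SAE is assessed as having a reasonable causal relationship, then it is defined as a SAR". For expectedness: "If the SAE is unexpected, then it is a SUSAR". Both bullets also refer back to the definition given, without saying which row of 17.1 is meant.

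Section 17.7 requires every SAE, whatever its cause, to be "reported to the sponsor (Joint Research Management Office) within 24 hours of the CI or co-investigators becoming aware of the event". Section 17.8 has the Chief Investigator review each SAE within 48 hours, including its relatedness and expectedness. Section 17.10 makes the Chief Investigator the sponsor's medical assessor.

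**The concern.** A SAR would normally be the serious subset of ARs, judged on the same causality test. Here the stricter test applies to the serious events, and fewer people can trigger it. An event can therefore be both serious and an adverse reaction in the protocol's own terms without being a serious adverse reaction. Section 17.2 does not settle this, because its SUSAR sentence has no causality condition.

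The classification has consequences. Under sections 17.7 and 17.10 and Appendix 1, SUSAR status leads to the sponsor's report to the MHRA, unblinding at the sponsor, and an unblinded individual case report to AstraZeneca. An SAE that is not a SUSAR goes to AstraZeneca in a quarterly blinded listing. Under section 28.0 the steering and safety committee sees no unblinded data unless it asks about an individual patient, so SUSAR handling is the main routine route by which a serious event is linked to allocation while the trial runs. AZD1656 is unlicensed, and these patients have competing explanations for serious events: recent surgery, immunosuppression, infection, rejection and diabetes. A judgement of possible but not probable is therefore plausible.

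**Working it through.** No arithmetic applies. The check takes events that are all serious and all unexpected, varies only the causality judgement, and reads each section literally.

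| Causality judgement | AR (17.1) | SAR (17.1) | SUSAR (17.1) | SUSAR (17.2, expectedness sentence) |
|---|---|---|---|---|
| A. Reporting investigator thinks it reasonably probable | Yes | Yes | Yes | Yes |
| B. Reporting investigator thinks it possible, not probable | Yes | No | No | Yes |
| C. Only the sponsor suspects a link | Yes | No | No | Yes |
| D. Both rule out a link | No | No | No | Yes |

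1. **Row A.** The sections agree.
2. **Row B.** The event meets the AR threshold, since a link is not excluded. It fails the SAR row, which asks for reasonable probability. The SUSAR row starts from a SAR, so it fails there too. Under the 17.2 sentence, an unexpected SAE is a SUSAR.
3. **Row C.** The AR row accepts the sponsor's judgement; the SAR row recognises only the reporting investigator's. The result is the same split.
4. **Row D.** The disagreement runs the other way: 17.2 read literally makes a SUSAR of an event that nobody attributes to treatment.

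The two bullets of 17.2 can also be read in sequence, so that the expectedness sentence applies only to events already classed as SARs. That removes the problem in row D. Row B then turns on what a reasonable causal relationship means. The phrase is close to the either-party sentence of the AR row, which favours the lower threshold, but the bullet refers back to 17.1, where the row actually headed SAR sets the higher one. Sections 17.7, 17.8 and 17.10 and Appendix 1 do not say which threshold governs.

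For a row B event, some handling is the same on either reading: the report to the sponsor within 24 hours, the Chief Investigator's review within 48 hours, entry in the quarterly listings and in the final unblinded listing, and inclusion in the annual risk-benefit review (section 18.0), which covers all events on the trial. Only the MHRA report, the unblinding at the sponsor that accompanies it, and the unblinded individual report to AstraZeneca differ.

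**The case against.** The best defence is that 17.2 is the working instruction and that neither of its sentences asks for probability. An assessor who follows it would class the row B event as a SAR, or directly as a SUSAR, and it would be expedited. The terms SUSAR and SSAR themselves speak of suspicion rather than probability. This part stands: the documents show a conflict between two sections, not a rule that such events escape. It does not remove the point, because 17.2 refers the assessor back to 17.1, and its SUSAR sentence catches the event only by dropping causality altogether.

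The investigator-versus-sponsor difference is also narrow in this trial. The Chief Investigator assesses causality, reviews every SAE and acts as the sponsor's medical assessor. Row C matters mainly when a co-investigator or delegated practitioner is the reporter. That stands too. The threshold difference in row B applies whoever reports.

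A reader might go further and infer that these events would be shown as unrelated in the SSAR listings and the annual safety report. The documents do not support that. Appendix 1 puts SAEs and SSARs in the same quarterly listings and requires reports to carry the investigator's causality assessment, so a view of possible can be recorded. It also requires emerging safety data to reach AstraZeneca within 24 hours.

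**Conclusion.** The point holds as an internal inconsistency in the safety-reporting definitions. For a serious, unexpected event judged possible but not probable, 17.1 says it is not a SUSAR and 17.2, read literally, says it is. Misclassification is possible, not certain. The exposure is limited to whether the event is reported to the MHRA as a SUSAR and sent unblinded as an individual report to AstraZeneca; it still reaches the sponsor as an SAE.

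The size cannot be put as a number of events. The documents give no expected SAE count, no split of causality judgements and no proportion unexpected, and the conclusion needs none of these. It rests only on reading the definitions as written.

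There is no effect on the primary endpoint, the sample size or the efficacy analyses. The safety comparison in section 11.5 counts AEs and SAEs by arm without using the causality label, so it is also unaffected. This is a modest but worthwhile correction for an unlicensed product.

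**What to change.** Make three linked edits so that one threshold and one set of judges run through AR, SAR and SUSAR.

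1. In 17.1, replace the SAR entry with: *an adverse reaction, as defined above, that is serious*. This carries over the AR row's own threshold and lets either the reporter or the sponsor make the judgement.
2. In the causality bullet of 17.2, use the same reasonable-possibility wording.
3. In the expectedness bullet of 17.2, make the SUSAR sentence start from an unexpected SAR instead of an unexpected SAE. Without this edit the two sections would still disagree about unexpected events that nobody attributes to treatment.

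The cost is a few lines of text, a note to staff delegated to assess SAEs, and the sponsor's decision on how to class the amendment. There may be a few more expedited reports than under a strict reading of 17.1, and fewer than under a literal reading of 17.2. Section 17.10 keeps the Chief Investigator blinded for SUSARs, so extra reports would not by themselves unblind the Chief Investigator.
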